**Follow up information should also be sent to all of the above.**

11.2.2.4 The DCP Medical Monitor and CCSA regulatory and safety staff will determine which SAEs require FDA submission as IND safety reports.

11.2.2.5 The Participating Organization will comply with applicable regulatory requirements related to reporting SAEs to the CIRB.

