6.8.2.6 Stratification Factors: None

## 6.9 Blinding and Unblinding Methods

Pre-registered participants will be assigned a unique subject number, e.g., an 8-character identification number, e.g. CPN00001. Participants will be randomized at registration on Day 1 to receive active intervention or placebo after they have satisfied the inclusion/exclusion criteria. For each participant, the sequence assignment will be determined according to a prepared randomization schedule at the time of registration/randomization. The assigned study agent bottle number generated for each randomized participant will be sent to the Thomas Jefferson University personnel. Pharmacy personnel will not be blinded to intervention arm assignment.

The study will be double-blinded until after specimen analysis to ensure that the participants, investigators, and clinic staff are unaware of the dosing assignment and to minimize potential for bias in study assessments or in reporting of AEs.

There are two distinct situations in which it will be deemed appropriate to break the randomization assignment for participants enrolled onto this current trial:

- In the event of an *emergency* for an individual participant.
- Serious Adverse Event (SAE) that fulfills the criteria for expedited reporting to the FDA.

In these situations, Participating Organization personnel may assume the participant is on active agent and call the CPN Registration Office within one business day to receive unblinding information. The study name/number, participant identifier, and participant initials will be required to break the randomization code. Thomas Jefferson University personnel are responsible for notifying the medical monitor at DCP, NCI of the unblinding event.

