#### **11.1.2 AE Data Elements:**

The following data elements are required for AE reporting.

- AE verbatim term
- NCI Common Terminology Criteria for Adverse Events version 4.0 (CTCAE v4.0) AE term (MedDRA lowest level term)
- CTCAE (MedDRA) System Organ Class (SOC)
- Event onset date and event ended date
- Treatment assignment code (TAC) at time of AE onset
- Severity grade
- Attribution to study agent (relatedness)
- Whether or not the event was reported as a SAE
- Whether or not the subject dropped due to the event
- Outcome of the event

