#### 11.2.2 Reporting SAEs to DCP

11.2.2.1 The Lead Organization and all Participating Organizations will report SAEs following the DCP SAE Reporting process: <http://prevention.cancer.gov/clinical-trials/clinical-trials-management/protocol-information-office/pio-instructions-and-tools/2012-consortia>.

Guidance for the process of coding the SAE can be obtained by contacting the NCI MD Help Desk: [[contact]](mailto:[contact])

11.2.2.2 Contact the DCP Medical Monitor by phone or email within 24 hours of knowledge of the event.

[name], D.O., M.Sc.  
National Institutes of Health, National Cancer Institute  
Division of Cancer Prevention  
[name]  
[name]  
[contact]  
Email: [[contact]](mailto:[contact])

Include the following information when contacting the Medical Monitor:

- Date and time of the SAE
- Date and time of the SAE report
- Name of reporter
- Call back phone number and email address
- Affiliation/Institution conducting the study
- DCP protocol number
- Title of protocol
- Description of the SAE, including attribution to drug

11.2.2.3 The Participating Organization will submit SAE reports to the following within 48 hours of learning of the event using the DCP SAE Reporting procedure:

1. **DCP Medical Monitor:** [[contact]](mailto:[contact])
2. **DCP's Regulatory Contractor CCS Associates, Inc.:** [[contact]](mailto:[contact])
3. **CPN Operations Office:** [[contact]](mailto:[contact])
4. **Synergy Pharmaceuticals:** [[contact]](mailto:[contact])

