### **13.7.1 Adverse Event Stopping Rule**

The trial will be monitored closely for occurrence of adverse events by the study team and by the Mayo Clinic Cancer Center Data Safety and Monitoring Board (DSMB) using the adverse event (AE) stopping rule specified below.

**Adverse Event Stopping Rule:** The stopping rule specified below is based on the knowledge available at study development. We note that the Adverse Event Stopping Rule may be adjusted in the event of either (1) the study re-opening to accrual after any temporary suspension or (2) at any time during the conduct of the trial and in consideration of newly acquired information regarding the adverse event profile of the treatment(s) under investigation. The study team in consultation with the Mayo DSMB may also choose to suspend accrual because of unexpected adverse event profiles that have not crossed the specified rule below.

Accrual will be temporarily suspended to this study if at any time we observe events considered at least possibly related to study treatment (i.e., an adverse event with attribute specified as "possible", "probable", or "definite") that satisfy any of the following criteria:

- If at any time, 1 or more subjects has experienced a Grade 4 or 5 adverse event at least possibly related to study drug.
- The study will be permanently stopped for any Grade 5 adverse event at least possibly related to study drug.

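### For SAEs that need an FDA report, section 6.9 lets unnamed site staff receive the unblinding information, although section 11.2.2.4 places that reporting decision with DCP and its contractor

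*Combined protocol and SAP*

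**What the plan says.** Section 6.9 allows the code to be broken in two situations. One is an emergency in an individual participant. The other is a "Serious Adverse Event (SAE) that fulfills the criteria for expedited reporting to the FDA". For both it gives a single procedure: "Participating Organization personnel may assume the participant is on active agent and call the CPN Registration Office within one business day to receive unblinding information". After that call, the site reports upward: "Thomas Jefferson University personnel are responsible for notifying the medical monitor at DCP, NCI of the unblinding event".

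Section 11.2.2.4 deals with who judges whether an SAE is reportable: "The DCP Medical Monitor and CCSA regulatory and safety staff will determine which SAEs require FDA submission as IND safety reports". It gives no time limit for that decision and no step by which the site learns the outcome.

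Section 6.6 says that site investigators and coordinators should remain blinded. Section 6.9 extends the blind to clinic staff until specimen analysis is done, and gives unbiased AE reporting as one of its purposes. Pharmacy personnel are the stated exception.

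Section 11.2.2.2 requires contact with the DCP Medical Monitor within 24 hours of knowledge of an SAE, and the listed content already includes attribution to the drug. Under section 11.2.2.3 the site must "submit SAE reports to the following within 48 hours of learning of the event".

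**The concern.** The two triggers in section 6.9 differ in who needs the answer. In an emergency the site may need to know the arm. For an FDA report, the parties that decide on the report are the DCP Medical Monitor and CCSA, and the protocol gives no reason for the site to know. Yet the same call route serves both triggers, and its recipient is the site.

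Attribution carries weight in this protocol. Section 13.7 uses it to define toxicity. Section 13.7.1 suspends accrual on "events considered at least possibly related to study treatment" once a single Grade 4 or 5 event qualifies, and stops the study permanently for a related Grade 5 event. If staff who rate relatedness know the arm, they may lean towards relating events on active and discounting events on placebo. The blind described in sections 6.6 and 6.9 is meant to prevent that.

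**Working it through.** No sample size, power or error rate enters this point. The check is a cross-reading, plus a comparison of deadlines.

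**Who decides and who receives the code**
- Reportability decision: DCP Medical Monitor and CCSA (11.2.2.4).
- Recipient of the unblinding information: Participating Organization personnel, not named by role (6.9).
- Direction of notice: from the site to the DCP medical monitor, after the break (6.9).
- Site staff meant to be blinded: investigators and coordinators (6.6), clinic staff (6.9).
- Person who assigns attribution: not named (11.1.4). The site supplies it in the 24-hour contact (11.2.2.2).

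So the site is given a trigger that it does not itself determine. It also obtains information that the deciding parties would use. Nothing in these sections restricts which site staff may receive it.

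**Whether attribution is fixed before the code is known**
- First attribution: due within 24 hours (11.2.2.2).
- Later change: follow-up reports are foreseen (11.2.2.3 and 11.2.3). Section 13.7 also reviews Grade 3 to 5 events first classed as unrelated or unlikely, in case a relationship emerges.
- Locking rule: none. No section requires attribution to be recorded before a code break, or the first rating to be kept beside a revised one.

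**Order of the deadlines**

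Assumptions: all clocks start when the site learns of the event (section 6.9 does not say so), there are no holidays, and learning times are spread evenly over the 168 hours of a week. Three readings of one business day were tried: 16:30 on the next business day (the close of Registration Office hours in section 6.8), midnight at the end of the next business day, and the same clock time on the next business day (end of Monday for weekend events).

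- Code deadline before the 48-hour report, midnight or same-clock reading: events learned of from Sunday to Thursday, 5 × 24 / 168 = 120/168, about 71%.
- Same comparison, 16:30 reading: the last 7.5 hours of Saturday are added, (120 + 7.5)/168 = 127.5/168, about 76%.
- For Friday events the order reverses under all three readings. For Saturday it reverses all day, or for 16.5/24 = 69% of the day with the 16:30 close.
- Code deadline before the 24-hour contact: 0% of the week under the midnight and same-clock readings. With the 16:30 close it is 5 × 7.5 / 168 = 37.5/168, about 22%.

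These are outer limits, so an earlier call is possible. In most of the week the first attribution falls due no later than the code call. The exposure is therefore an early call made on the site's own judgement, or a later revision of attribution.

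**Scale**
- One break reveals 1/24 = 4.2% of participants, all at one site (13.3).
- Section 2.2.2 reports no SAE in the multiple-dose study, which lists 60 + 7 = 67 subjects on active.

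**The case against.** The strongest reply has four parts.

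- **The wording is permissive and the recipient open.** Section 6.9 says personnel may call. The caller could be a pharmacist who already knows the arm, and the protocol does not say that the person rating relatedness receives the code. This stands as a limit: unblinding of an AE assessor is allowed, not stated. But section 6.9 does not confine the call to unblinded staff, and its wording covers anyone at the site.
- **If the site waits for the DCP/CCSA decision, attribution is already with DCP.** This is right for the first rating. It does not cover an early call or a revised rating.
- **Other checks exist.** Section 13.7 re-examines severe events rated unrelated or unlikely, and section 13.7.1 lets the study team and DSMB suspend accrual before the rule is crossed. These reduce the consequence of a biased rating. They do not keep the site blinded.
- **Unseen documents may settle it.** Sections 11.2.2.1 and 12.4 refer to a DCP reporting process and a master monitoring plan. Either might set recipient and order, but section 6.9 would still need to agree with them.

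Two stronger readings are tempting. A reader might infer that the code always reaches the site before the written SAE report is due. The documents do not support this: the clock in section 6.9 has no stated start, the order reverses for Friday and most or all Saturday events, and attribution is due earlier, at 24 hours. A reader might also infer from the required field "Treatment assignment code (TAC) at time of AE onset" in section 11.1.2 that every AE form reveals the arm. That section only names a data element. It does not say that the code is arm-specific, and a masked value is the reading consistent with sections 6.6 and 6.9.

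**Conclusion.** The mismatch is real and should be corrected. For the FDA-reporting trigger, section 6.9 routes unblinding information to unspecified site personnel, while section 11.2.2.4 gives the reporting decision to others and sections 6.6 and 6.9 intend the site to stay blinded. At a single site, AE assessors can learn an arm without an emergency, and attribution can then be revised with that knowledge.

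The expected impact is small. It needs an SAE that meets expedited criteria, a call by someone who also assesses AEs, and an attribution that changes as a result. The documents give no rate for that sequence, and none is estimated here. One break shows one participant's assignment, and the primary endpoint is a laboratory cGMP measurement.

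A reader might infer that any unblinded SAE could by itself halt the trial. Section 13.7.1 does not say that: the event must be Grade 4 or 5 and at least possibly related, whereas an SAE under section 11.2.1 can be a hospital stay for a lower-grade event.

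The conclusion assumes that the personnel in section 6.9 can include staff who assess AEs, and that no unseen procedure overrides that section.

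**What to change.** Reconcile section 6.9 with section 11.2.2:

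- **Recipient.** For the FDA-reporting trigger, the CPN Registration Office releases the code only to the DCP Medical Monitor and CCSA. Site unblinding is kept for the separate emergency trigger.
- **Order.** The site's attribution is recorded before any non-emergency release. It is kept and shown alongside any later revision in the section 13.7 summaries.

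Which rating should govern the section 13.7.1 rule is left open. Using only the blinded rating is debatable, since an event on placebo could then stop the trial.

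The cost is a few sentences of protocol text and one extra call route for the Registration Office. Sample size, visits and the primary analysis do not change.

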11.2.3 Follow-up of SAE

Site staff should submit follow-up reports as requested when additional information is available. Follow-up information should be sent to DCP, CCS Associates, and the CPN Operations Office as soon as available. SAEs will be treated according to institutional standards of good clinical practice and followed to resolution.

## **12. STUDY MONITORING**

### **12.1 Data Management**

The Mayo Clinic Cancer Center database will be the database of record for the protocol and subject to NCI and FDA audit. Minimum Data Sets will be submitted to DCP per contract requirements. Please see CPN Master Data Management Plan.

### **12.2 Case Report Forms**

Participant data will be collected using protocol-specific case report forms (CRF) utilizing NCI-approved Common Data Elements (CDEs). The approved CRFs will be used to create the electronic CRF (e-CRF) screens for data entry into the Mayo Clinic Cancer Center database. Amended CRFs will be submitted to the DCP Protocol Information Office for review and approval.

### **12.3 Source Documents**

A source document is any document, form, or record where *specific participants'* data are first recorded. FDA [21 CFR 312.62 (b)] requires that the investigator "...prepare and maintain accurate case histories designed to record all observations and other data pertinent to the investigation on each individual treated with the investigational agent or employed as a control in the investigation."

Among many other items, source documents include:

- Inpatient and outpatient medical records

- Progress notes
- Consults
- Nursing notes
- Pathology reports
- Endoscopy reports
- Medicine/radiation administration records
- Surgical reports
- Laboratory reports
- Admission forms
- Flow sheets and worksheets that are signed and dated
- Protocol or study road maps
- Appointment books
- Participant diaries/calendars
- Blood and tissue collection/submission requisition forms (signed and dated).

#### **12.4 Data and Safety Monitoring Plan (DSMP)**

The CPN Master DSMP is applicable to all studies within the CPN Consortium and provides detailed information regarding data and safety monitoring for this study. The trial will be monitored closely for occurrence of adverse events by the study team and by the Mayo Clinic Cancer Center Data Safety Monitoring Board (DSMB). The DSMB (along with the study Medical Monitor) will be consulted regarding whether or not accrual should be suspended to allow for investigation in the occurrence of severe adverse events, particularly for those that are possibly, probably, or definitely related to the study agent.

Additionally, the DSMB (along with the study Medical Monitor) will be consulted regarding whether or not accrual should be suspended to allow for investigation if 25% or more of participants who begin intervention fail to undergo the post-intervention flexible sigmoidoscopy.

#### **12.5 Sponsor or FDA Monitoring**

The NCI, DCP (or their designee), pharmaceutical collaborator (or their designee), or FDA may monitor/audit various aspects of the study. These monitors will be given access to facilities, databases, supplies and records to review and verify data pertinent to the study.

#### **12.6 Record Retention**

Clinical records for all participants, including CRFs, all source documentation (containing evidence to study eligibility, history and physical findings, laboratory data, results of consultations, *etc.*), as well as IRB records and other regulatory documentation will be retained by the Investigator in a secure storage facility in compliance with Health Insurance Portability and Accountability Act (HIPAA), Office of Human Research Protections (OHRP), Food and Drug Administration (FDA) regulations and guidances, and NCI/DCP requirements, unless the standard at the site is more stringent. The records for all studies performed under an IND will be maintained, at a minimum, for two years after the approval of a New Drug Application (NDA). For NCI/DCP, records will be retained for at least three years after the completion of the research. NCI will be notified prior to the planned destruction of any materials. The

records should be accessible for inspection and copying by authorized persons of the Food and Drug Administration. If the study is done outside of the United States, applicable regulatory requirements for the specific country participating in the study also apply.

## **12.7 Clinical Trials Agreement (CTA)**

Agent(s) used in this protocol is/are provided to the NCI under a Clinical Trials Agreement (CTA) between Synergy Pharmaceuticals, Inc. and the NCI Division of Cancer Prevention. Therefore, the following obligations/guidelines, in addition to the provisions in the “Intellectual Property Option to Collaborators” contained within the terms of award, apply to the use of Agent(s) in this study:

12.7.1 Agent(s) may not be used for any purpose outside the scope of this protocol, nor can Agent(s) be transferred or licensed to any party not participating in the clinical study. Collaborator(s) data for Agent(s) are confidential and proprietary to Collaborator(s) and shall be maintained as such by the investigators. The protocol documents for studies utilizing investigational agents contain confidential information and should not be shared or distributed without the permission of the NCI. If a participant on the study or participant’s family member requests a copy of this protocol, the individual should sign a confidentiality agreement. A suitable model agreement can be downloaded from the DCP website.

12.7.2 Clinical Trial Data and Results and Raw Data developed under a collaborative agreement will be made available exclusively to Collaborator(s), the NCI, and the FDA, as appropriate. All data made available will comply with HIPAA regulations.

12.7.3 When a Collaborator wishes to initiate a data request, the request should first be sent to the NCI, who will then notify the appropriate investigators of Collaborator's wish to contact them.

12.7.4 Any manuscripts reporting the results of this clinical trial must be provided to DCP for immediate delivery to Collaborator(s) for advisory review and comment prior to submission for publication. Collaborator(s) will have 30 days (or as specified in the CTA) from the date of receipt for review. Collaborator shall have the right to request that publication be delayed for up to an additional 30 days in order to ensure that Collaborator’s confidential and proprietary data, in addition to Collaborator(s)’s intellectual property rights, are protected. Copies of abstracts must be provided to DCP for forwarding to Collaborator(s) for courtesy review as soon as possible and preferably at least three days prior to submission, but in any case, prior to presentation at the meeting or publication in the proceedings. Press releases and other media presentations must also be forwarded to DCP prior to release. Copies of any manuscript, abstract, and/or press release/ media presentation should be sent to:

DCP Protocol Information Office  
E-mail: [name]

The Protocol Information Office will forward manuscripts to the DCP Project Officer for distribution to the Collaborator(s). No publication, manuscript or other form of public disclosure shall contain any of Collaborator’s confidential/proprietary information.

## **13. STATISTICAL CONSIDERATIONS**

### **13.1 Study Design/Description**

Twenty-four (24) participants (12 per arm) will be randomized to dolcanatide 27 mg versus matching placebo (once daily for a period of 7 days). The primary endpoint will be a direct comparison of the pharmacological effect on cGMP levels for dolcanatide arm vs. placebo. Secondary endpoints will compare the Pharmacodynamic (PD) Response rate and adverse events between arms.

### **13.2 Randomization/Stratification**

Participants will be registered on Day 1 after they have satisfied the inclusion/exclusion criteria. All participants will have been assigned a unique subject number [e.g., 7-character subject identification]. Twelve patients will be randomized to each arm (24 total; dolcanatide or placebo, where participants will be treated once daily for a period of 7 days).

### **13.3 Accrual and Feasibility**

We estimate that we will need to screen 40 and pre-register up to 30 participants for eligibility in order to obtain the expected number of registered participants. Participants will be enrolled from a single site (Thomas Jefferson University). This study will enroll 24 participants (12 per arm). With an expected average randomization rate of 4 participants per month, this study is anticipated to require a maximum of 7 months to complete the determination of the primary endpoint. This includes periods during which enrollment traditionally lags, such as holidays.

It is noteworthy that the CRU at Thomas Jefferson University Hospital has achieved 100% enrollment for healthy volunteers in all previous phase I and phase II studies. This has included healthy volunteer studies involving bone marrow biopsy, adipose biopsy, right heart catheterization, and skin biopsy. The CRU has also conducted a number of upper endoscopy studies, including a recent study that employed three endoscopies per subject with direct bile collection for pharmacokinetic evaluation. Based on our previous studies performed in the CRU at Thomas Jefferson University Hospital, an expected screen fail rate is 1:1. This estimation includes, but not limited to, the exclusion of the underlying diseases, positive drug response during screening, or height or weight limitations. Such studies are typically limited to patients younger than 50 years of age. Given the higher age range in the current study and a slightly higher screen fail rate noted in our prior endoscopy study, we expect to have to screen 40 to end up with 24 evaluable for the primary endpoint in this study. Time to study completion, including data entry, clean-up, and analysis, is approximately 1.0 year from study activation.

